5.2 Primary, secondary and exploratory endpoints

Primary endpoints for primary objectives A1 and A2:

- Maternal primary endpoint 1: Occurrence of solicited local reactions within 7 days following administration of investigational product (pain at the injection site, redness, and swelling).
- Maternal primary endpoint 2: Occurrence of solicited systemic events within 7 days following administration of investigational product (fever, nausea/vomiting, diarrhoea, headache, fatigue/tiredness, muscle pain, and joint pain).
- Maternal primary endpoint 3: Occurrence of solicited and unsolicited adverse events through 1 month after administration of investigational product.
- Maternal primary endpoint 4: Occurrence of SAEs, MAEs, and obstetric complications (peripartum, intrapartum, and postpartum) throughout the study (Visit 1 through the 12month post-delivery study visit) and any unsolicited events leading to study withdrawal.
- Infant primary endpoint 1: Occurrence of unsolicited adverse events from birth to 6 weeks of age

A placebo controlled clinical trial investigating the safety and immunogenicity of GBS6 in pregnant women with and without human immunodeficiency virus (HIV) infection and their infants

Protocol Version 5.0, Dated 01/02/2023

Protocol Version/date 5.0,01/02/2023
R&D Protocol Code Number:
Page:28

- Infant primary endpoint 2: Occurrence of SAEs, AEs of special interest (major congenital anomalies, developmental delay, and suspected or confirmed GBS infection), and MAEs through 12 months of age and any unsolicited events leading to study withdrawal.

Secondary endpoints for secondary objectives B1, B2, B3:

- Maternal secondary endpoint 1: GBS serotype- specific IgG antibody titres measured at baseline, 2 weeks, 1 month after vaccination, at delivery and 6 weeks after delivery in HIV positive and HIV negative women.
- Maternal secondary endpoint 2: GBS serotype specific IgG titres measured at baseline, and at delivery in HIV positive and HIV negative women.
- Infant secondary endpoint 1: GBS serotype specific IgG antibody titres in HIV-exposed and unexposed infant participants measured at birth, 18 weeks and 12 months of life.
- Infant secondary endpoint 2: GBS serotype specific IgG titres in HIV-exposed and unexposed infant participants measured at 18 weeks of life.
- Infant secondary endpoint 3: Placental transfer ratio of GBS-specific antibodies in HIV-exposed and unexposed pregnancies.

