6.3 Statistical methods

Safety data will be analysed separately for maternal participants and their infant participants.

- Descriptive analysis

A flowchart will be used to summarise the number of mothers approached, consented, recruited, assigned to the different study arms, receiving the intended vaccines, completing the study protocol and analysed for the primary outcome, as recommended by the CONSORT statement (<http://www.consort-statement.org/>).

- Statistical significance and confidence intervals

A placebo controlled clinical trial investigating the safety and immunogenicity of GBS6 in pregnant women with and without human immunodeficiency virus (HIV) infection and their infants

Protocol Version 5.0, Dated 01/02/2023

Protocol Version/date 5.0,01/02/2023
R&D Protocol Code Number:
Page:33

MAKERERE UNIVERSITY
SCHOOL OF MEDICINE
APPROVED AMENDMENT
Valid Until

★ 30 NOV 2023 ★

RESEARCH & ETHICS COMMITTEE
[name]

5% significance will be used and 95% confidence intervals.

- Statistical software

Statistical analyses will be performed on STATA version 15 or similar.

- Missing data

Analysis will be by modified intention to treat (mITT), meaning individuals are analysed according to the group they are randomised to, but only those with at least one blood taken and antibody result will be included, with missing data (e.g. from withdrawals, non-compliers) assumed missing at random. Missing data will be excluded from relevant analyses. The mITT analysis will include blood samples taken outside the recommended timing. A per-protocol analysis will also be performed if there are major protocol deviations. Spurious data will be checked to source records and investigated but included if no cause is identified.

- Outliers, censored data and non-normal data

Outliers will be included in the analyses and investigated assuming no errors have occurred. We will assign all results of <2 a value of 1 for calculation of geometric means. Antibody concentrations will be log-transformed for analyses of mean antibody levels.

- Statistical analysis for each objective and outcome

Statistical Analysis of primary endpoints

The followings are the primary analyses for each of the outcomes related to primary objectives.

- Maternal primary endpoint 1:

Proportion of maternal participants reporting solicited local reactions within 7 days following administration of GBS6 vaccine will be calculated with exact binomial 95% confidence

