A placebo controlled clinical trial investigating the safety and immunogenicity of GBS6 in pregnant women with and without human immunodeficiency virus (HIV) infection and their infants

Protocol Version 5.0, Dated 01/02/2023

Protocol Version/date 5.0,01/02/2023
R&D Protocol Code Number:
Page:34

intervals for each group. Comparison between groups (GBS v Placebo within each HIV strata) will be by Fisher's exact test.

- Maternal primary endpoint 2:

Proportion of maternal participants reporting solicited systemic events within 7 days following administration of GBS6 vaccine will be calculated with exact binomial 95% confidence intervals for each group. Comparison between groups (GBS v Placebo within each HIV strata) will be by Fisher's exact test.

- Maternal primary endpoint 3:

Proportions of maternal participants reporting solicited and unsolicited adverse events through 1 month following administration of GBS6 vaccine will be calculated with exact binomial 95% confidence intervals for each group. Comparison between groups (GBS v Placebo within each HIV strata) will be by Fisher's exact test.

- Maternal primary endpoint 4:

Proportions of maternal participants with SAEs, MAEs, and obstetric complications (peripartum, intrapartum, and postpartum) throughout the study (Visit 1 through the 12-month postdelivery study visit) and any unsolicited events leading to study withdrawal following administration of GBS6 vaccine will be calculated with exact binomial 95% confidence intervals for each group. Comparison between groups (GBS v Placebo within each HIV strata) will be by Fisher's exact test.

- Infant primary endpoint 1:

Proportions of infants with unsolicited adverse events from birth to 6 weeks of age month following administration of GBS6 vaccine will be calculated with exact binomial 95% confidence intervals for each group. Comparison between groups (GBS v Placebo within each HIV strata) will be by Fisher's exact test.

A placebo controlled clinical trial investigating the safety and immunogenicity of GBS6 in pregnant women with and without human immunodeficiency virus (HIV) infection and their infants

Protocol Version 5.0, Dated 01/02/2023

Protocol Version/date 5.0,01/02/2023
R&D Protocol Code Number:
Page:35

- Infant primary endpoint 2:

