8.1. Inclusion criteria for Maternal Participants

1. Age ≥ 18 to ≤ 40 years of age, inclusive at day of signing the ICF.
2. Pregnant at ≥ 27 0/7 to ≤ 35 6/7 gestation on the day of planned vaccination, verified by ultrasound scan (U/S).
3. Low risk, singleton pregnancy, as assessed by the study physician based on ultrasound scan and previous obstetric history.
4. Documented negative HBV surface antigen, HCV antibody, and syphilis tests at screening.
5. Normal full blood count (CBC), renal and liver function tests at screening.
6. Documented HIV test during pregnancy undertaken as per the national guidelines.
7. If HIV infected pregnant women, stable on ART for at least 2 months prior to study start with an undetectable viral load (VL)
8. Determined by medical history, physical examination, screening laboratory assessment, and clinical judgment to be appropriate for inclusion in the study.
9. Receiving prenatal standard of care including HIV care if applicable at the clinics/physician offices/hospital network affiliated with the clinical study site.
10. Willing to give birth at Kawempe Specialised National Referral Hospital, Kawaala or Komamboga Health Centre III or Wakiso or Kisenyi Health center IV, Uganda.

A placebo controlled clinical trial investigating the safety and immunogenicity of GBS6 in pregnant women with and without human immunodeficiency virus (HIV) infection and their infants

Protocol Version 5.0, Dated 01/02/2023

Protocol Version/date 5.0,01/02/2023
R&D Protocol Code Number:
Page:41

11. Willing and able to participate for the duration of the study visits and follow-up until 12-months post-delivery.
12. Willing and able to be contacted by telephone for the full duration of the study, and to give informed consent for their infant participant to participate in the study.

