11.1.2 Visit 1- Vaccination (Day 1) Visit

- Review laboratory results.
- Ensure that the participant continues to be eligible for the study, meets none of the participants withdrawal criteria as described in Section 11.4, and meets none of the temporary delay criteria as described in Section 8.6.1.
- Prior to vaccination, measure vital signs, including weight, oral temperature, sitting blood pressure and pulse rate, and respiratory rate.

A placebo controlled clinical trial investigating the safety and immunogenicity of GBS6 in pregnant women with and without human immunodeficiency virus (HIV) infection and their infants

Protocol Version 5.0, Dated 01/02/2023

Protocol Version/date 5.0,01/02/2023
R&D Protocol Code Number:
Page:61

- Perform a targeted physical examination, evaluating any clinically significant abnormalities based on history and the participant's self-reported symptoms or complaints since the last visit.
- Perform obstetric examination including but not limited to fundal height, foetal heart tones, and foetal movement.
- Obtain urine sample for glucose and protein testing (urine dipstick).
- Issue the participant a paper diary card and provide instructions on its completion. Ensure that the participant records a baseline assessment of prompted systemic events in the paper diary card prior to vaccination.
- Prior to vaccination, collect a blood sample of approximately 10 mL for immunogenicity assessments and approximately 5 mL for CD4 count and viral load for HIV positive participants.
- Prior to vaccination, obtain one rectal and one vaginal swab for GBS microbiological culture.
- The unblinded dispenser dispenses the investigational product.
- The blinded administrator administers a single 0.5-mL injection of investigational product into the deltoid muscle, preferably of the nondominant arm.
- Blinded site staff must observe the participant for at least 30-minutes after investigational product administration for any acute reactions. Record any acute reactions in the participant's source documents and on the AE page of the CRF, and on an SAE form as applicable.
- Issue a measuring device to measure local reactions and a digital thermometer for recording daily temperatures, and provide instructions on their use.
- Ask the participant to complete the paper diary card from Day 1 to Day 7 (Day 1 is the day of vaccination).

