13.1 Participant paper diary card

The responsible research nurse/clinician will be asked to monitor and record local reactions reported by the participant, as well as, systemic events, including fever, and antipyretics/pain medication used to prevent and/or treat symptoms, within a fixed time window each day for 7 days following vaccination (where Day 1 is the day of vaccination) on a system that uses a personal digital assistant (PDA) or other technology. A baseline assessment (nausea/vomiting, diarrhea, headache, fatigue/tiredness, muscle pain, or joint pain over the previous month) prior to vaccination will be recorded in the paper diary card. This system, hereafter referred to as the participant's paper diary card, allows recording of these assessments only within a fixed time window, thus providing the accurate representation of the participant's experience at that time. Data on local reactions, systemic

A placebo controlled clinical trial investigating the safety and immunogenicity of GBS6 in pregnant women with and without human immunodeficiency virus (HIV) infection and their infants

Protocol Version 5.0, Dated 01/02/2023

Protocol Version/date 5.0,01/02/2023
R&D Protocol Code Number:
Page:88

events, and antipyretics/pain medication used to prevent and/or treat symptoms reported on the paper diary card will be uploaded manually entered into REDCap, where they will be available for review by investigators, their qualified designees, and sponsor staff at all times via an internet-based portal. At intervals agreed to by the sponsor, these data will be transferred electronically for analysis and reporting. These data do not need to be reported by the investigator in the CRF. However, if a participant withdraws because of prompted events reported in the paper diary card, the event(s) should be recorded on the AE page of the CRF, regardless of whether the investigator considers the event(s) to be clinically significant.

Investigators (or appropriately qualified designee) are required to review the paper diary card data online to evaluate participant compliance and as part of the ongoing safety review.

The investigator or designee must contact the participant in order to obtain stop dates for any reactions ongoing on the last day that the paper diary card was completed. The stop dates should be documented in the source documents and the information entered in the CRF.

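### The primary comparison for maternal endpoint 2 does not use the pre-vaccination symptom record that the trial collects, so it is valid but less sensitive than it could be

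*Protocol*

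**What the plan says.** The endpoint in Protocol section 5.2 is "Occurrence of solicited systemic events within 7 days following administration of investigational product (fever, nausea/vomiting, diarrhoea, headache, fatigue/tiredness, muscle pain, and joint pain"), which is seven symptom types. Section 6.3 introduces its list with "The followings are the primary analyses for each of the outcomes related to primary objectives", so what follows is fixed as primary. For endpoint 2 it reads "Proportion of maternal participants reporting solicited systemic events within 7 days following administration of GBS6 vaccine will be calculated", with an exact binomial interval in each group, and then: "Comparison between groups (GBS v Placebo within each HIV strata) will be by Fisher's exact test". No baseline term appears. The section sets the level with "5% significance will be used and 95% confidence intervals".

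The baseline record is required in two places. Section 11.1.2 (Visit 1) instructs staff: "Ensure that the participant records a baseline assessment of prompted systemic events in the paper diary card prior to vaccination". Section 13.1 specifies the content: "A baseline assessment (nausea/vomiting, diarrhea, headache, fatigue/tiredness, muscle pain, or joint pain over the previous month) prior to vaccination will be recorded". Those six items are exactly the endpoint's components other than fever. The schedule of activities repeats the requirement.

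The protocol assigns the baseline record no analytic role. Section 6.3 closes by leaving detailed and additional exploratory analyses to the SAP, which is not at hand.

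**The concern.** Women are vaccinated late in pregnancy: "Pregnant at ≥ 27 0/7 to ≤ 35 6/7 gestation on the day of planned vaccination". Fatigue, nausea, headache and muscle pain may well be present at that stage whatever is injected. Each woman who would report a symptom in the 7 days anyway counts as an event in either arm, which shrinks the difference that the vaccine can produce.

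A pre-vaccination record of the same symptoms is the natural covariate for separating this background from a vaccine effect. Collecting it and then fixing an unadjusted test leaves that information out of the main tolerability comparison. In a safety trial, low sensitivity means a real excess of systemic reactions is more easily missed.

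**Working it through.** **The plan's own binary safety figure.** Section 6.1 states 80% power for prematurity, 10% v 22%, with 300 in total (150 per arm). With the normal approximation and two-sided 5%, power = Φ[(0.12√150 − 1.96√(2×0.16×0.84)) / √(0.10×0.90 + 0.22×0.78)] = Φ[(1.470 − 1.016)/0.511] = 81.2%. The stated figure reproduces. The protocol gives no power figure for endpoint 2.

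**Inputs.** 75 v 75 within each HIV stratum and a 5% level (section 6.3; two-sided assumed). All symptom rates below are assumptions, because the documents give none.

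**Step 1: dilution.** Let b be the 7-day background rate and v the probability that the vaccine causes a symptom, assumed independent of background. Then P(event | vaccine) = 1 − (1−b)(1−v), and the risk difference is v(1−b). Fisher power by exact enumeration:

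| b | v=20%: difference, power | v=30%: difference, power |
|---|---|---|
| 10% | 18 points, 76% | 27 points, 97% |
| 30% | 14 points, 37% | 21 points, 71% |
| 50% | 10 points, 21% | 15 points, 42% |
| 70% | 6 points, 10% | 9 points, 19% |

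The direction is clear. The size depends on an unstated b.

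**Step 2: what stratifying recovers.** Let q be the share symptomatic at baseline, and b1 and b0 the 7-day background rates with and without a baseline symptom, so b = q·b1 + (1−q)·b0. In stratum k, with T women, n1 vaccinated, n0 on placebo, m events and a events among the vaccinated, the Mantel-Haenszel statistic is [Σ(a − n1·m/T)]² / Σ[n1·n0·m(T−m)/(T²(T−1))], referred to 3.84. The unadjusted chi-square test is included to separate the effect of baseline from Fisher's conservatism. Results in % from 20,000 simulated trials per row:

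| q; b1/b0; v | Fisher | Chi-square | Mantel-Haenszel | Gain over Fisher | Gain from baseline |
|---|---|---|---|---|---|
| 60%; 80/20; 0 (null) | 3.9 | 5.5 | 4.6 | n/a | n/a |
| 60%; 80/20; 30% | 33.2 | 39.3 | 49.5 | 16.3 | 10.2 |
| 50%; 70/10; 30% | 57.1 | 62.1 | 73.9 | 16.8 | 11.8 |
| 30%; 40/10; 20% | 53.5 | 60.2 | 64.1 | 10.6 | 3.9 |
| 60%; 50/30; 30% | 54.5 | 59.2 | 58.8 | 4.3 | −0.4 |
| 60%; 50/40; 30% | 47.8 | 53.6 | 51.3 | 3.5 | −2.3 |
| 90%; 60/30; 30% | 31.9 | 38.3 | 38.0 | 6.1 | −0.3 |
| 95%; 60/20; 20% | 15.1 | 19.4 | 19.1 | 4.0 | −0.3 |

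The stratified test beats the planned Fisher test in every non-null row, by about 4 to 17 points. The part due to baseline runs from about −2 to +12. It disappears when baseline predicts weakly (50/30, 50/40) or is saturated (90-95% symptomatic). A very strong predictor would give more: at q=50%, 85/10, v=30%, the gain over chi-square is 21 points. Nothing in the documents supports so strong a link, least of all with a one-month recall, so the range quoted leaves it out.

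**The case against.** The best reply is that nothing here is an error. An any-event proportion with a concurrent randomised placebo arm is a valid analysis. Section 6.1 calls the analyses largely descriptive, with a sample size set by what the site can achieve, and claims no power for this endpoint. The SAP may use the baseline, and the gain rests on assumed rates.

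Most of that stands, and it rules out several stronger readings that a reader might infer:

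- *That the comparison is biased.* It is not, because the placebo arm carries the same background. Only each arm's raw proportion includes symptoms that women already had.
- *That the trial never uses the baseline.* This cannot be shown without the SAP. A supportive table of events new or worse than baseline is ordinary SAP content, and its absence here is no finding.
- *That background symptoms are strongly predicted by baseline.* The documents do not say so. The recall covers a month and the endpoint covers 7 days, so prediction may be weak.
- *That new-or-worse events cannot be derived.* Section 13.1 gives the recall window but not how the baseline is graded. The windows differ; whether the scales differ is not stated.

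The reply does not cover the test itself. Section 6.3 does more than describe: it names a significance test as primary for this endpoint, and a more sensitive one is available from data already required.

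**Conclusion.** The point holds as an avoidable loss of sensitivity in a stated primary test. Section 6.3 fixes an unadjusted Fisher comparison for maternal endpoint 2, while sections 11.1.2 and 13.1 require a baseline record of all six non-fever components. Under the assumed rates, the stratified test gains about 4 to 17 points of power per HIV stratum over the planned test, at a type I error of about 5%. About −2 to +12 points of that come from baseline, and the remainder from replacing a conservative exact test. The result rests on assumed background rates, an assumed strength of prediction and a vaccine effect independent of background. It does not call the planned comparison invalid.

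**What to change.** In section 6.3, maternal primary endpoint 2:

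- Keep the any-event proportion with its exact 95% interval for each group.
- Replace the Fisher comparison with a Mantel-Haenszel test and risk difference, GBS6 v placebo within each HIV stratum, stratified by the recorded baseline symptom (yes/no). Use the same symptom for per-symptom comparisons, and any of the six for the composite. Fever has no baseline item, so the comparison of fever alone stays unstratified.

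Stratifying keeps every woman and every event. Counting only new-onset events would not be a safe substitute: at v=20% and b=70%, with half the background present at baseline, it gives 9% power against 10% for the raw count.

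The cost is a few lines of text. The downside is a loss of up to about 2 points against an unadjusted chi-square test if baseline proves uninformative.

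Optionally, for women not yet dosed, add a diary line covering the 7 days before vaccination on the Table 4 grades, and keep the one-month item so that all women share one stratifier. Women already dosed would have only the one-month recall.

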Proportions of infants with SAEs, AEs of special interest (major congenital anomalies, developmental delay, and suspected or confirmed GBS infection), and MAEs through 12 months of age and any unsolicited events leading to study withdrawal following administration of GBS6 vaccine will be calculated with exact binomial 95% confidence intervals for each group. Comparison between groups (GBS v Placebo within each HIV strata) will be by Fisher's exact test.

Statistical analysis of secondary endpoints

The followings are the primary analyses for each of the outcomes related to secondary objectives.

- Maternal secondary endpoint 1:

Antibody levels for GBS serotype-specific antibody concentrations measured at baseline, 2 weeks, 1 month after vaccination, at delivery, and 6 weeks after delivery in HIV positive and HIV negative women will be described using box-and-whisker plots with a log-scale y-axis. GMTs of GBS serotype specific antibody concentrations measured at baseline, 2 weeks, 1 month after vaccination, at delivery, and 6 weeks after delivery in HIV positive and HIV negative women will be calculated with 95% confidence intervals post vaccinations and the groups will be compared using unpaired t-tests or the Kruskal Wallis test if log-titres are not normally distributed.

Reverse cumulative distribution curves (RCDCs) of antibody concentrations by vaccine groups will be generated for each GBS6 serotype. Additionally, graphs of geometric means and the associated 95% CIs of the antibody concentrations will be presented at each analysis time point by vaccine group and serotype. The proportions of participants achieving defined GBS6 serotype specific IgG concentrations will be summarised descriptively at prespecified time points as counts and percentages with 2-sided 95% exact CIs by vaccine group and HIV

A placebo controlled clinical trial investigating the safety and immunogenicity of GBS6 in pregnant women with and without human immunodeficiency virus (HIV) infection and their infants

Protocol Version 5.0, Dated 01/02/2023

Protocol Version/date 5.0,01/02/2023
R&D Protocol Code Number:
Page:36

MAKERERE UNIVERSITY
SCHOOL OF MEDICINE
APPROVED AMENDMENT
Valid Until

★ 30 NOV 2023 ★

RESEARCH & ETHICS COMMITTEE
[name]

status. Groups 1 vs 2, 3 v 4 will be compared by a t-test or Kuskal-Wallis test if logged data are not normally distributed.

- Maternal secondary endpoint 2:

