14.10. Definition of Medically attended Adverse events

An MAE is defined as a non-serious AE that results in an evaluation at a medical facility. MAEs will be assessed from screening for all participants up to Visit 9 for maternal participants and up to Visit 6 for infant participants.

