15.6. Benefits to participants

The mothers and babies involved in the study will also have the benefit of meeting with and ask questions of experienced study team clinical staff for the duration of their enrolment. Morbidity will be closely monitored as a safety net for participants, and free access to basic health care will be provided to the mothers and their child. This includes basic medical treatment for non-severe infections (urinary, respiratory, malaria, skin infections etc.) provided at any of the study hospitals (open 24 hours). In most cases, if the family incurs costs at referring facilities or out of hours centres, these costs will be reimbursed by the study team. The free health care will be provided to our participants until the child is 12 months of age, (including participants subsequently excluded) as well as 24/7 access to study staff via mobile phones.

A placebo controlled clinical trial investigating the safety and immunogenicity of GBS6 in pregnant women with and without human immunodeficiency virus (HIV) infection and their infants

Protocol Version 4.0, Dated 11/05/2022

ProtocolVersion/date 5.0, 01/02/2023
R&D ProtocolCodeNumber:
Page:113

16. Data Management and sharing

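### Maternal primary endpoint 4 and infant primary endpoint 2 are analysed only as ever/never proportions: section 6.3 does not say whether the listed categories are pooled, and repeat medically attended events are discarded

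*Protocol*

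**What the plan says.** Section 6.3 presents these methods as the primary analyses for the primary objectives.

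- The second infant primary endpoint is analysed as "Proportions of infants with SAEs, AEs of special interest (major congenital anomalies, developmental delay, and suspected or confirmed GBS infection), and MAEs". The window and last component are "MAEs through 12 months of age and any unsolicited events leading to study withdrawal".
- Maternal primary endpoint 4: "Proportions of maternal participants with SAEs, MAEs, and obstetric complications (peripartum, intrapartum, and postpartum) throughout the study", with the window given as "Visit 1 through the 12-month postdelivery study visit". Events leading to withdrawal are added.
- For both, the proportions "will be calculated with exact binomial 95% confidence intervals for each group", and Fisher's exact test compares GBS6 with placebo within each HIV stratum. Sections 6.1 and 9.3 give 75 women per group.

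No count, rate or person-time measure is named for either endpoint. The end of section 6.3 leaves detailed analyses to the SAP.

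Section 14.10 says: "An MAE is defined as a non-serious AE that results in an evaluation at a medical facility". Section 14.12 leaves out visits not associated with an adverse event. Section 15.6 says that "free access to basic health care will be provided to the mothers and their child" until the child is 12 months old. Sections 14.5.1 and 14.5.2 keep MAE reporting open to the last visit for mothers and infants.

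**The concern.** There are two separate weaknesses.

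First, each endpoint puts unlike categories in one sentence and attaches one summary and one test to it. An analyst could compute a single any-event proportion. Non-serious illness visits would then share a numerator with SAEs, congenital anomalies and GBS infection, and a difference in the rarer categories would be diluted. Such a pool would also mix harms with GBS infection, which the vaccine is meant to prevent.

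Second, even with separate lines, an MAE can happen several times to one participant. A woman or infant with one MAE counts the same as one with five. If vaccination changed how often participants fall ill, much of that information would not reach the planned test.

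These are primary safety endpoints in what section 4.8 calls the first evaluation of GBS6 in HIV-infected pregnant women.

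**Working it through.** **The plan's own safety figure.** Section 6.1 claims 80% power for prematurity at 10% v 22%, 300 women in total. With 150 per arm and mean rate 0.16:

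- null SE = √(2 × 0.16 × 0.84 / 150) = 0.0423
- alternative SE = √((0.10 × 0.90 + 0.22 × 0.78) / 150) = 0.0418
- z = (0.12 − 1.96 × 0.0423) / 0.0418 = 0.89, so power = 81%

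The figure reproduces. The protocol gives no power or expected rate for MAEs, SAEs, AEs of special interest (AESIs) or these two endpoints, so every event rate below is an assumption. All tests are two-sided 5% at 75 v 75.

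**If the categories were pooled.** With the same MAE proportion m in both arms, independent of SAEs at proportion s, the pooled proportion is 1 − (1 − m)(1 − s). Exact Fisher power for SAEs of 5% v 15%:

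| MAE proportion m | Pooled proportions | Power |
|---|---|---|
| 0 (SAEs alone) | 5.0% v 15.0% | 44% |
| 10% | 14.5% v 23.5% | 22% |
| 30% | 33.5% v 40.5% | 11% |
| 60% | 62.0% v 66.0% | 6% |

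For example, at m = 30%: 1 − 0.70 × 0.95 = 0.335 and 1 − 0.70 × 0.85 = 0.405.

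**If the categories are separate: MAEs ever/never against MAE rate.** Assume one year of follow-up, r MAEs per year on placebo and 1.5r on vaccine.

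- Probability of at least one MAE: 1 − exp(−r) for Poisson counts, or 1 − (1 + kr)^(−1/k) with dispersion k. Fisher power is by exact enumeration.
- Rate ratio: log 1.5 = 0.405, with variance (1/75)(1/r + 1/(1.5r) + 2k). Power is approximately Φ(0.405/SE − 1.96). Example, r = 1 and k = 0: SE = √(1.667/75) = 0.149, 0.405/0.149 = 2.72, Φ(0.76) = 78%.
- The last column simulates a log rate-ratio test with variance estimated from the data (20,000 trials per row).

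| r per year | k | Ever/never | Fisher | Rate ratio, formula | Rate ratio, simulated |
|---|---|---|---|---|---|
| 0.5 | 0 | 39% v 53% | 34.5% | 48% | 50% |
| 1 | 0 | 63% v 78% | 42.5% | 78% | 78% |
| 2 | 0 | 86% v 95% | 34.2% | 97% | 97% |
| 0.5 | 0.5 | 36% v 47% | 24.4% | 39% | 40% |
| 1 | 0.5 | 56% v 67% | 27.0% | 57% | 58% |
| 2 | 0.5 | 75% v 84% | 21.3% | 74% | 74% |

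Under no difference, the simulated rate test rejected in about 5% of trials in these scenarios. Simulated powers can move by a point or so between runs.

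The rate comparison has more power in every row, including those at 0.5 and 1 per year where the ever/never proportion is well short of a ceiling. The gain comes mainly from using repeat events.

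**The case against.** The strongest reply is that nothing here is an error. Section 6.1 calls the analyses largely descriptive and the sample size a matter of what is achievable. Incidence proportions with exact intervals over a common planned follow-up are valid in a randomised trial. Which category gets its own table line is ordinary SAP content. This has weight and keeps the point modest. However, section 6.3 already fixes the measure and the test as primary, so the choice can be reviewed here.

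A reader might infer three stronger things that the protocol does not support.

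- **That MAEs swamp SAEs and AESIs as planned.** Section 6.3 never says that the categories are combined. The plural proportions fits one proportion per category, although infant endpoint 1 also uses the plural for a single category. MAEs are non-serious by definition, and AESIs and SAEs have definitions of their own. On the separate reading the dilution disappears. What limits SAE detection is then 75 per group: with 5% on placebo, about 21% on vaccine is needed for 80% power. SAEs are also reported to the sponsor within 24 hours (section 14.1), and related ones trigger a stopping rule (section 8.7).
- **That the MAE proportion will be near its ceiling.** No MAE rate is given, and section 14.12 excludes visits without an adverse event. Free care makes repeat illness visits plausible but does not establish saturation.
- **That partly followed participants are dropped.** Section 6.3 does say "Missing data will be excluded from relevant analyses", but in a paragraph that defines the analysis set by antibody results. Section 6.2 puts every dosed woman and every enrolled infant in the safety population, and section 8.6 keeps data up to withdrawal unless the participant asks otherwise.

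**Conclusion.** The point holds in a limited form. Section 6.3 leaves open whether the listed categories form one composite, and it names only an ever/never measure for MAEs.

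For a 50% rise in MAEs from 0.5 to 2 per year, the planned test has roughly 21% to 43% power, against 40% to 97% for a rate ratio on the same events. This rests on assumed rates, one year of follow-up per participant and dispersion of 0 or 0.5. Mothers are followed for longer, since their window starts at vaccination.

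The fall from 44% to 11% or 6% for SAEs applies only if the categories are pooled. It also assumes independence and equal MAE proportions in the two arms. It is a reason to rule pooling out in writing and does not show that pooling is planned.

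**What to change.** In section 6.3, for maternal primary endpoint 4 and infant primary endpoint 2:

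1. State that SAEs, each AESI, obstetric complications, MAEs and events leading to withdrawal are each tabulated and compared separately in the safety population, with no pooled test.
2. Keep the MAE proportion and add the MAE event rate per person-time by group. Give a rate ratio and 95% CI from a model robust to overdispersion, such as negative binomial or quasi-Poisson with log follow-up time as offset.

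The cost is one extra model-based analysis and a few more table lines. MAEs are already recorded at each visit, so no new visit or sample is needed. The case report form should allow each MAE to be counted as its own event.
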